## Acronyms

AIDS	Acquired Immune Deficiency Syndrome
ANC	Antenatal care
ART	Antiretroviral Therapy
C-Saúde	Centro pela Saúde Global
CCR	Child-at-risk Clinic
CFPS - HCB	Center of Training and Research in Beira Central Hospital (“Centro de Formação e Pesquisa em Saúde – Hospital Central de Beira”)
CI	Confidence interval
CPM	Cumulative probability model
DPS-Z	Provincial Directorate of Health of Zambézia (“Direção Provincial de Saúde-Zambézia”)
EPTS	Electronic patient tracking system
FGH	Friends in Global Health
GoM	Government of Mozambique
HCW	Health care worker(s)
HIV	Human Immuno-deficiency Virus
MBWR	Mindfulness-based wellness and resilience
MOH	Ministry of Health
MPR	Medication possession ratio
NGO	Non-governmental organization
NID	Patient identification number
NIMH	National Institute of Mental Health
NIOZ	Operational Investigation Committee of Zambézia (“Núcleo de Investigação Operacional de Zambézia”)
PEPFAR	United States President's Emergency Plan for AIDS Relief
PI	Principal Investigator
PLHIV	Person/People Living with HIV
PSS	Psychosocial Support
RCT	Randomized controlled trial
SOC	Standard of care
SSA	sub-Saharan African
VL	Viral load
VUMC	Vanderbilt University Medical Center
WHO	World Health Organization

## 2. Funding

This project will be funded by a National Institute for Mental Health (NIMH) R34 award (PI. [name]).

#### 4. Introduction and Justification

**The setting.** Friends in Global Health (FGH), a Vanderbilt University Medical Center (VUMC)-affiliated non-governmental organization (NGO), partners with the Ministry of Health (MOH) to provide clinical support to currently 149 health care facilities in the province. As of October 2024, all activities transitioned to the newly established national organization C-Saúde (please see footnote above). Evidence-based interventions address barriers to treatment retention by emphasizing a more patient-centered approach via community antiretroviral therapy (ART) distribution points, adherence clubs, home-based and spaced refill visits, and employing community health workers (CHW) for ART provision and education. Despite these efforts, only 87% of people who test HIV-positive remain in care at 12 months (FGH program data, March 2023).

**Who is struggling with ART adherence?** People with low levels of education, living in poverty, and under 35 years old have lower rates of retention and adherence to treatment in Mozambique, similar to trends in other sub-Saharan African (SSA) countries.

**Interventions have attempted to address social, financial, and educational barriers.** A review of qualitative factors impacting ART adherence in SSA yields examples of social (HIV stigma, poverty stigma), individual (trust, health beliefs), and structural (health care organizations, delivery, costs) factors serving as barriers to HIV treatment adherence. Stigma can influence adherence, particularly if someone has not disclosed their HIV status to their family. A combination of interventions in Mozambique, including the employment of peer educators, availability of psychological counseling services, and local media campaigns have led to Moral Trauma Protocol, Version 1.3; PI: [name], 27 September 2024

decreased stigma and increased HIV knowledge both among people living with HIV (PLHIV) and community members, but enacted stigma within intimate partner relationships remains a concern, particularly among women. Men have historically been less willing to attend clinical services at health facilities, seen as women-dominated spaces, given the association of health facilities with childbirth and related perinatal services. Male engagement in antenatal care services, including HIV counseling and testing, has led to dramatic increases in HIV testing and treatment initiation among men, but retention remains an issue. Male-friendly clinics have been piloted (based on a Kenyan model) with a focus on offering male health providers, extended hours services, and supportive health care that goes beyond HIV to reduce potential stigma and provide socially acceptable treatment services for men. Recently these clinical were expanded to anyone who needed services beyond the daytime, allowing anyone working to attend clinical appointments. Additionally, community adherence support groups, created to reduce the frequency of medication pick-up visits (which are often financially and logically challenging for patients) have been successfully employed among some patients in Mozambique to overcome these barriers. Despite these efforts, patient retention remains sub-optimal. What can we do? We can start by listening to PLHIV who are receiving care in and to health care workers (HCW) who are providing services to PLHIV in these communities.

**Patients report experiencing poor quality health care, including rude behavior by providers.** This poor quality care includes perceived punishment (e.g., making patients wait excessively long before being attended to) for using traditional medicine, verbally abusing patients for not understanding instructions/directions, refusing to treat patients who lose their HIV registration card, and ignoring patient concerns about treatment side effects or opportunistic infections. Our team has documented that poor treatment experienced by patients at the health facility (HF) appears to be fueled by two factors: (1) multiple stigmas (including HIV stigma) directed at the patient population, and (2) provider burnout and dissatisfaction with their jobs.

**Health care worker burnout is a global crisis.** Burnout among health care providers in SSA is common. Health care provider burnout can be defined as “a long-term stress reaction marked by emotional exhaustion, depersonalization, and a lack of sense of personal accomplishment.” Clinician burnout across SSA is an urgent problem, with more than 62% of providers in Malawi, between 21% - 72% in South Africa, and 23- 51% in Zambia experiencing burnout. Delivery of quality health care services in extremely resource-limited settings can be grueling for front line health care providers. Frequent stock outs of essential medications, a lack of qualified clinicians to assist in treating the long queue of patients, providers assigned to communities with different languages/cultures than their own (there are 43 different languages spoken in Mozambique), and insufficient infrastructure can be overwhelming for even the best-trained and motivated providers. Health care workers facing unfamiliar and challenging work environments are also at risk for moral injury in their workplace, which “can occur when someone engages in, fails to prevent, or witnesses acts that conflict with their values or beliefs.” Experiences that are morally injurious may contribute to negative consequences in one’s own behavior, attitude, and/or well-being. In SSA, there is little formal psychosocial support for health care providers based at health facilities. Given that many providers live alone (with spouses and children based in large cities), there is often a lack of built-in family support in the locations where providers work. This isolation and lack of support can compound provider exhaustion, which may manifest as excessive frustration with patients who miss appointments, do not pick up medications on time, lose their identification cards, or challenge provider treatment recommendations. While the U.S. President’s Emergency Plan for AIDS Relief Moral Trauma Protocol, Version 1.3; PI: [name], 27 September 2024

(PEPFAR), the Global Fund, and Mozambican government funds are being employed to improve quality of care, and while these health systems experience slow, incremental improvements, we have the obligation and opportunity to study interventions that address provider well-being, including job satisfaction, burnout, and emotional stability.

**HIV-related stigma among health care workers results in poor patient outcomes.** There have been recent calls to address the pressing issue of HIV stigma in the health system. HIV stigma is pervasive in SSA at multiple levels, including systemic, interpersonal, and internal. Perceived community- or health facility-level stigma influences internalized stigma, which results in poorer treatment outcomes, social isolation, and poorer quality of life among PLHIV. HIV stigma is largely driven by misconceptions about HIV transmission (i.e., fear of contracting HIV while treating an HIV-positive patient), lack of awareness about the negative impact stigma has on PLHIV, perceived moral transgressions made by those living with HIV (e.g., the person brought their diagnosis upon themselves), and pre-existing negative attitudes towards marginalized groups more likely to contract HIV. If patients perceive their clinicians to hold negative attitudes towards them due to their HIV status or their association with another marginalized group (e.g., those who are poor, seek care from traditional medicine, do not understand the germ theory of disease), they are less likely to adhere to medication and remain in care.

**Summary of background and potential of *Trabalhamos Juntos (We Work Together)*.** We propose to pilot a novel intervention that provides health care workers the skills, confidence, and support structures necessary to improve clinical care delivery, leading to increased retention and adherence to ART in Mozambique. Health care providers need the correct tools to reduce prejudice and sustain empathetic and sympathetic health care delivery in under-capacitated health facilities. The combination of an intervention to address provider burnout and an intervention to address stigmatizing attitudes towards patients will ensure that PLHIV receive the best possible care.

## 5. Objectives

The overall goal of this project is to assess the impact of two health care worker interventions designed to improve the mental health and well-being of health care workers in Zambézia Province, Mozambique.

Our specific objectives are as follows:

**Objective 1: Evaluate the impact of resilience training only, anti-stigma training only, and resilience and anti-stigma training (vs. standard of care) on hypothesized mechanisms of behavior change among health care workers through a pilot cluster randomized controlled trial (RCT).**

*Hypothesis 1: We hypothesize that health care workers who participate in this training will report a significant reduction in stigmatizing attitudes towards their patients, increased resilience, decreased emotional exhaustion, and decreased depersonalization of their patients.*

**Objective 2: Investigate the impact of health care worker training to reduce stigma and increase wellness and resilience on patient adherence to HIV treatment and satisfaction with health services.**

*Hypothesis 2: We hypothesize that patients receiving care at the site randomized to both resilience and anti-stigma training will have increased adherence to medication (as determined by proportion of time on medication and self-report) at 6 months, higher rates of viral suppression at 6 months, and increased satisfaction at 6 months.*

**Objective 3: Assess experience of moral trauma depression, anxiety and suicidal ideation among health care workers, and explore the perspectives of services/ interventions that could support those at risk of or experiencing moral trauma.**

*Hypothesis: We hypothesize that understanding the experiences and suggestions on mitigating will support development or improvement of interventions that increase wellbeing of health care workers. We will also capture baseline moral injury among health care workers as well as depression, anxiety, and suicidal ideation among health care workers at 10-11 months post intervention.*

## 6. Design and Study Questions

We propose to conduct a pilot cluster randomized controlled trial to evaluate the effects of our interventions. Four health care facilities in Zambézia Province will be selected and then randomized to the control (standard-of-care [SOC]) or the intervention arms (anti-stigma training ONLY, resilience training ONLY, or anti-stigma + resilience trainings) (i.e., there will be one control arm and three intervention arms).

**There are six specific study questions:**

**Question 1:** Does our resilience/wellness intervention improve health care worker mental health outcomes?

**Question 2:** Does our anti-stigma intervention reduce stigma towards patients?

**Question 3:** Do health care workers who receive these interventions have suggestions about how they could be improved?

**Question 4:** Do our interventional trainings have any impact on patient adherence to HIV treatment?

**Question 5:** Do HCW in this area experience or have risk for moral injury/ moral trauma, and what services/interventions do HCW think could be supportive if experiencing this?

**Question 6:** Do HCW in this area experience depression, anxiety or suicidal ideation?

## 7. Study Population

**a. Population:**

1. PLHIV: Adult individuals enrolled in HIV care and treatment at one of the study sites.
2. Health Care Workers: Physicians, nurses, medical technicians, health counselors, community health care workers, and other clinical and non-clinical (e.g., receptionists, data entry clerk) staff who are providing health services to adult PLHIV.

**b. Inclusion/Exclusion Criteria:**

1. PLHIV (for medical file review)

Inclusion:

- Adult individuals, 18 years of age or older
- Active in care (i.e., not in default)
- Receiving HIV care and treatment at one of the four study sites.

2. PLHIV (for survey participation)

Inclusion:

- Adult individuals, 18 years of age or older
- Active in care (i.e., not in default)
- Receiving HIV care and treatment at one of the four study sites.
- Sought care at health facility on the day of survey data collection

Exclusion (for survey participation only):

- Any clinical or mental condition (for example, but not limited to: patients with delusions, hallucinations, impaired cognitive function, mental retardation, medical condition with physical deterioration, or under the influence of drugs or alcohol at the time of study recruitment), that as per the investigator's opinion/assessment, would preclude provision of informed consent or make study participation unsafe or unethical;
- Being at the health facility for reasons other than their own medical appointment and/or picking up their own medication;
- Those who do not have routine care at the selected health facility (e.g., individuals who receive HIV care and treatment at a different facility than their own due to stigma or other reasons).

3. Health Care Workers

Inclusion:

- Adult individuals, 18 years of age or older;
- working as physicians, nurses, medical technicians, health counselors, community health care workers, or other clinical and non-clinical staff (e.g.,

receptionists, data entry clerk) who provide health services to adults living with HIV at one of the four study sites;

- willing to be followed as a study participant during the 6-month study period, and does not intend to transfer to another HF during the study period (per investigator's assessment at time of recruitment), as self-reported.
- Be able to read and write in Portuguese, as self-reported.

Exclusion:

- Those who are not permanent members of the health facility staff (i.e., floating providers that work at multiple sites in a given week);
- Any clinical or mental condition, including influence of drugs or alcohol at the time of study recruitment, that as per the investigator's opinion/assessment, would preclude provision of informed consent or make study participation unsafe or unethical;
- Individuals working in the health facility but from the following cadres: drivers, security personnel, and workers who do not have any patient-facing roles.

**c. Calculations of Sample Size:**

**Objective 1:** Each of the four selected sites have no more than 25 health care workers providing HIV care, so we anticipate a maximum total of 100 health care workers equally divided between each intervention arm and the control arm. With  $n=25$  in all arms, assuming an intraclass correlation coefficient (ICC)=0.10, and two-sided type I error rate of 0.05, then we anticipate that we will have approximately 80% power to detect a difference of 1.07 standard deviations of the outcome (e.g., change in resilience score between baseline and after intervention), or the change in stigma score between baseline and after intervention) between the intervention vs. control for each of the two interventions. If ICC=0.05 (or 0.15), then we will have approximately 80% power to detect a difference of 0.85 (or 1.26) standard deviations.

For our qualitative interviews, we will continue to collect data until we have reached data saturation. Based on similar interviews conducted in 2022 (unpublished, IRB# 99/CIBS-Z/22), we believe we will reach saturation with no more than 40 interviews.

**Objective 2:** Each of the four health facility sites serve at least 4,000 patients enrolled on ART who will be scheduled for clinic visit(s) during the study period. With a minimum of  $n=4,000$  in each facility, assuming an ICC=0.05, and two-sided type I error rate of 0.05, then we anticipate that we will have approximately 80% power to detect a difference of 0.64 standard deviations of the outcome (e.g., proportion of time on medication) between the intervention vs. control. If ICC=0.025 (or 0.10), then we will have approximately 80% power to detect a difference of 0.45 (or 0.91) standard deviations.

The survey will be done in a sub-population of the cohort of HIV-positive patients at all four sites. Due to the exploratory nature, sample sizes for the patient surveys were not calculated based on existing assumptions. We estimate that 80 surveys per HF ( $n=320$ ) will provide us with the requisite baseline preliminary data on how they experience health care. For outcome

measures available on only these surveyed participants, we anticipate approximately 80% power to detect differences of 0.55, 0.71, and 0.96 standard deviations of the outcome assuming ICC of 0.025, 0.05, and 0.10, respectively.

**Objective 3:** For the qualitative interviews for this objective, we will collect data until we have reached data saturation. Based on similar interviews conducted in 2022 (unpublished, IRB# 99/CIBS-Z/22), we believe we will reach saturation with between 20-40 interviews, with no more than 40 interviews. For the surveys related to anxiety, depression and suicidal ideation the goal is to reach all of those involved in our baseline assessments, 100 health care workers.

**d. Sampling**

1. PLHIV participants: All adults receiving HIV care and treatment at the study sites will be included (including from adult care services sector, antenatal care [ANC] sector, Child-at-Risk Clinic [CCR], and those receiving joint TB/HIV care services). We aim to have a similar proportion of males and females, and from the different sectors.
2. Health care worker participants: All health care workers who are eligible will be invited to participate in the study. We will focus on identifying participants from different sectors (HIV, TB, maternal health) and levels (nurses, medical technicians, physicians, etc.) and aim to have a similar proportion of males and females.

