#### **Objective 2:**

With Objective 2 most of our outcomes are continuous measurements, and analyses will be similar to those described above: linear mixed effects models that take advantage of the factorial nature of outcome, with clusters defined as study sites, and unadjusted and adjusted for a small number of PLHIV-level covariates (age, sex, educational level, marital status, language, duration on ART, and history of ART medication pick-ups within the previous 6 months). For binary outcomes (e.g., undetectable viral load), we will fit generalized linear mixed effects models with a logit link function.

Every patient is given 30, 60, 90, or 180 days to pick up their ART medication, as indicated in the medical charts. If a patient picks up medication after the indicated/scheduled date, they will be considered "non-adherent" for each day after their specific pick-up date; this will be assessed over the course of the 6-month follow-up and will be treated as a continuous variable (a proportion between 0 and 1 for each participant). Participants who are lost to follow-up from the health facility during the 6-month follow-up period will be considered "non-adherent" for the days that they are lost. For persons who die or are known to have transferred care outside of the catchment area, the proportion of time on medication will be computed using only time prior to death or transfer of care. For our primary retention outcome (proportion of time on medication), normality assumptions are unlikely to hold, perhaps even after data transformation. Hence, we will fit a cumulative probability model (CPM) with fixed effects for the clinics. The CPM is well-suited for this setting because it does not require symmetry/normality in the outcome (which is bounded between 0 and 1 and likely not normal); in the absence of covariates, it reduces to the Wilcoxon rank sum test. The CPM has been shown to perform well in settings investigating medication adherence. Specifically, the distribution of the proportion of time on medication will be modeled as

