## Appendix 2: Survey Questions (Objective 2: PLHIV surveys)

### **Sociodemographic data (to be collected at each survey instance)**

- a. Age (years)
- b. Sex
- c. Highest educational level
- d. Marital status
- e. What is your maternal language (language you grew up with)
- f. Patient ID
- g. Year in which you began HIV care at this health facility

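### The patient survey aims for a mix of care sectors but does not record sector, so the mix cannot be checked and can only partly be adjusted for

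*Combined protocol and SAP*

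**What the plan says.** Section 7.d (Sampling), item 1, begins "All adults receiving HIV care and treatment at the study sites will be included" and lists four sources: "including from adult care services sector, antenatal care [ANC] sector, Child-at-Risk Clinic [CCR], and those receiving joint TB/HIV care services". It then adds "We aim to have a similar proportion of males and females, and from the different sectors". It gives no number, tolerance or order of priority, and does not say which group of patients the aim governs.

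For the survey, section 7.c states "We estimate that 80 surveys per HF" (320 in all) and claims "approximately 80% power to detect differences of 0.55, 0.71, and 0.96 standard deviations of the outcome" at ICCs of 0.025, 0.05 and 0.10. Section 7.e recruits by convenience as patients leave the facility. Section 8.a allows the baseline and endline respondents to be different people. Section 7.b excludes from the survey anyone "Being at the health facility for reasons other than their own medical appointment and/or picking up their own medication".

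The Objective 2 models in section 10 adjust for "age, sex, educational level, marital status, language, duration on ART, and history of ART medication pick-ups within the previous 6 months". The Appendix 2 form collects age, sex, education, marital status, maternal language, patient ID and the year care began. Appendix 10 lists eight fields for survey participants. Sector appears in none of these three places. Appendix 9, the extract for all patients, includes pregnancy status, TB treatment and patient ID.

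**The concern.** The plan treats sector as important enough to sample on, but provides no means of seeing it afterwards. Sector plausibly bears on the survey outcomes. The satisfaction items ask about the provider, and section 7.d, item 2, itself distinguishes staff by HIV, TB and maternal health, so sector may determine which staff a patient is rating.

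Each arm is one facility. If one site's respondents come largely from antenatal care and another's from general adult care, the difference in who was asked becomes part of the comparison between arms. Adjusting for sex does not remove it, because much of the relevant contrast is among women: those in antenatal or Child-at-Risk care against those in general adult care. Satisfaction is named in Hypothesis 2, and the section 15 timeline uses the survey to assess the interventions' impact, so the comparison will be read even though the survey is exploratory.

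**Working it through.** **1. The plan's own power figures.** Take two sites against two, with 80 respondents per site. The effective number per side is 160/(1 + 79 × ICC). The detectable difference is solved from a two-sample t-test at two-sided 0.05 and 80% power. The 0.05 is stated for the Objective 2 cohort and assumed to carry over to the survey.

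| ICC | Effective n per side | Recomputed (SD) | Stated (SD) |
|---|---|---|---|
| 0.025 | 160/2.975 = 53.8 | 0.545 | 0.55 |
| 0.05 | 160/4.95 = 32.3 | 0.708 | 0.71 |
| 0.10 | 160/8.90 = 18.0 | 0.962 | 0.96 |

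The stated figures reproduce, and the present point does not alter them.

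**2. What the aim can govern.** The chart review takes all eligible adults, so its mix is whatever the clinics have. Only the 80 survey respondents per facility can be steered.

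**3. Can both aims be met?** Read literally, equal sectors means 80/4 = 20 respondents in each, and equal sexes means 40 women. Take antenatal respondents as all women, and let *c* be the female share of Child-at-Risk respondents. The documents do not give *c*. The number of women among the 40 adult-care and TB respondents is then 40 − 20 − 20*c* = 20(1 − *c*).

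| Assumed *c* | Women among the 40 adult-care and TB respondents |
|---|---|
| 0.5 | 10 |
| 0.7 | 6 |
| 0.9 | 2 |
| 1.0 | 0 |

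Both aims can be met in every row, but the adult-care and TB respondents become increasingly male.

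Conversely, suppose sectors are equal and nobody steers on sex. The overall female share is 0.25 + 0.25*c* + 0.5*a*, where *a* is the female share in adult care and TB. With *a* = 0.4 and *c* = 0.9 it is 0.25 + 0.225 + 0.20 = 67.5%. With *a* = 0.6 and *c* = 1.0 it is 0.25 + 0.25 + 0.30 = 80%. The two aims pull in different directions, and the plan does not say which should yield.

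**4. Size of an unadjusted mix difference.** The shift between two sites is the sector gap times the difference in mix. Neither is in the documents, so both are assumed: gaps of 0.2 to 0.5 SD and mix differences of 10 to 50 percentage points.

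- Smallest: 0.2 × 0.10 = 0.02 SD, which is 0.02/0.71 = 3% of the detectable difference at ICC 0.05.
- Largest: 0.5 × 0.50 = 0.25 SD, which is 0.25/0.71 = 35% of it.
- In the two-versus-two analysis, a single deviating site is averaged with one other, so the shift halves to 0.01 to 0.125 SD.

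For scale, the between-site SD implied by the plan's ICCs is √0.025 = 0.16, √0.05 = 0.22 and √0.10 = 0.32 SD. The SD of a difference between two single sites is √2 times these: 0.22, 0.32 and 0.45. For a two-versus-two contrast, the site component has SD √(σ²/2 + σ²/2) = σ, so 0.16 to 0.32.

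**5. What can be recovered.** Pregnancy status approximates antenatal care, and TB treatment approximates TB/HIV care. Both are in Appendix 9 but not Appendix 10. Using them means linking survey patient ID to an extract that sections 10 and 11 describe as de-identified, so linkage is not assured. Child-at-Risk care has no good proxy in either list.

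**The case against.** The strongest reply is that this is a soft aim in an exploratory survey. The wording asks for similar proportions and sets no quota. Sex is recorded and adjusted for. The routine-data list in section 8.a is explicitly open-ended, so sector might be extracted. Mix could drift because of exit convenience sampling even if the sentence in section 7.d were deleted. The largest shift requires one site to ignore sectors while another equalises them. All of that stands, and it keeps the point small. It does not explain how a sector aim is to be verified when no listed field holds sector.

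Three stronger readings are tempting, and the documents do not support them:

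- **That the sex and sector aims contradict each other.** An allocation of 40 women in antenatal and Child-at-Risk care and 40 men in adult and TB care meets both.
- **That no woman in general adult care would be surveyed.** This needs exactly equal sectors and sexes, and an all-female Child-at-Risk group. The plan states neither. The own-visit rule in section 7.b limits who can be surveyed there but says nothing about their sex.
- **That an uneven mix could not be corrected at all.** Appendix 9 allows partial recovery if linkage is possible.

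**Conclusion.** The point holds as a gap in measurement and adjustment. The survey has a sector aim, a recruitment method that lets sector mix vary by site and round, and no sector variable with which to check or adjust for it. The possible shift is about 0.02 to 0.25 SD between two sites, or 0.01 to 0.125 SD in the factorial contrast if one site deviates. These figures rest wholly on the assumed sector gaps and mix differences. Nothing in the documents suggests that the mix would follow the arm, so the shift could go either way.

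The consequence is confined to satisfaction, medical mistrust and perceived provider stigma. The chart-based outcomes and the stated survey power are unaffected. A reader might infer that the survey comparison is invalid. The documents do not support that: the shift is no larger than the ordinary site differences that the plan's middle ICC already implies. The case for acting is that recording sector costs almost nothing.

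**What to change.** - Add one item to Appendix 2, asked in both rounds: sector attended today.
- Add sector to the covariates of the adjusted survey models in section 10, Objective 2.
- Report the sector-by-sex mix of respondents for each site and round.
- State in section 7.d that the mix aim applies to the survey and is to be applied in the same way at every site and in both rounds.

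The cost is one survey question and three model degrees of freedom (four sectors less one).

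Appendix 4 already quotes results from the staff survey, so a patient round may also be complete. For any such round, use the Appendix 9 pregnancy and TB fields in a sensitivity analysis where linkage allows, and state that Child-at-Risk care cannot be identified.

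Fixed sector-by-sex quotas are not needed for this point. They would require attendance figures by sector, which the documents do not give, and would replace the convenience recruitment. That is a separate design choice.
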